Recommendations are made in writing to the study investigators. The DSMC are given blinded trial data, but may request unblinding if safety data warrant. The initial review includes a review of the following items: statement of the protocol design, characteristics of the study data collection site, inclusion/exclusion criteria, randomization plan, definition of participants (e.g., screened, enrolled, randomized, treated, drop-out, lost to follow-up), intervention definition, dosage and frequency of study drug, reasons to discontinue study or to terminate individual participants, reasons to discontinue treatment, outcome measures, sample size target, key adherence and safety variables, and the data analysis plan.

Subsequent ongoing reviews include: enrollment data, including those screened, enrolled, and active; subject eligibility; demographic characteristics of participants (total, and by group), recruitment and retention (total and by group). Protocol compliance are evaluated by reviewing: the expected recruitment rate, study drop-outs and reasons for leaving the study, data quality assurance reports, overall data flow procedures, CRFs collected, received, and entered; protocol deviations; protocol violations; missing data; staff omissions; subject refusal to provide data; adherence to stopping rules. The data safety report are provided in total and by group, and include any relevant medical, psychosocial or laboratory data, AEs summarized in tables, individual SAE reports, concomitant medications, and concomitant illnesses. The outcome data report includes outcome data analyzed by group, masked or unblended, with or without statistical analyses, and include all outcome variables.

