DURATION OF SUBJECT PARTICIPATION AND DURATION OF STUDY	Subjects will be on study for up to 9 months Screening: up to 30 days Treatment: 3 months Follow-up: 6 months The total duration of the study is expected to be nine months. One month for subject recruitment and nine months for final subject participation and follow-up.
CONCOMITANT MEDICATIONS	Allowed: standard therapy Prohibited: current use of/ dependence on any opioid medication or current naltrexone treatments.
EFFICACY EVALUATIONS	
PRIMARY ENDPOINT	
 • To detect 27% reductions in numbers of binge drinking occasions, as well as 10% reductions in the average numbers of drinks on drinking days among treatment arm compared to placebo arm.
SECONDARY ENDPOINTS	
 • To detect 15-23% reductions in the urine positivity rate in the treatment arm compared to the placebo arm.
OTHER EVALUATIONS	Potential biomarkers for alcohol: EtG and PEth
SAFETY EVALUATIONS	Change in clinical safety labs from baseline to week 12 Incidence of adverse events
PLANNED INTERIM ANALYSES	No planned interim analyses. Serious adverse events will be monitored by the committee on an ongoing basis throughout the study.

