8.2 Blinding

Due to the objectives of the study, the identity of test and control treatments will not be known to investigators, research staff, or patients. The following study procedures will be in place to ensure double-blind administration of study treatments.

- Access to the randomization code will be strictly controlled.
- Packaging and labeling of test and control treatments will be identical to maintain the blind.

The study blind will be broken on completion of the clinical study and after the study database has been locked.

During the study, the blind may be broken **only** in emergencies when knowledge of the patient's treatment group is necessary for further patient management. When possible, the Investigator should discuss the emergency with the Medical Director prior to unblinding.

Describe the procedures for unblinding.

[figure not shown]
At the end of the study, the biostatistician will provide us with which study drug kits were naltrexone treatment and which study drug kits were placebo. The study drug kits will be compared to the participant enlisted in the study. Study Staff will inform the participant verbally of their study treatment assignment. For those who do not respond by phone, a letter will be sent to their address to inform the participant of their treatment assignment.

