14 DATA SAFETY MONITORING

The PI along with the site physician [name], will be responsible for ensuring proper monitoring of the safety and efficacy of this trial, including the execution of the DSM plan, and complying with the reporting requirements, including reports to the IRB, DSMB, NIDA and (where applicable) the FDA (see Figure 1 below).

The research team including the PI, clinicians, data manager, research associates, and recruitment coordinator, meets weekly to discuss all aspects of the study such as recruitment and retention, clinical or counseling issues, and any regulatory or operation issues. All study documents are monitored by the study coordinator for quality assurance on a weekly basis to ensure timely

corrections to charting such as missing initials or cross-outs with error-correction. Although there is no outside monitor, the clinicians review each other's charts for accuracy, consistency, and adherence to protocol. Regular audits will be conducted as well on consent forms, laboratory logs and other data collection forms.

The interim DSMB report will contain a brief description of the trial, baseline socio-demographic characteristics of participants, retention and disposition of study participants, a description of any quality assurance or regulatory issues, a report of AEs and SAES, and the status of outcome data.

Members and affiliation: We will use the existing University of California, Los Angeles (UCLA) Data & Safety Monitoring Board for Addiction Medicine (DSMBAM), which has extensive experience in monitoring pharmacologic interventions, including among vulnerable populations. The DSMBAM has monitored all of our pharmacologic trials for substance users.

To ensure that the DSMB oversight of the study remains independent from the proposed study, the PI([name]) as well as others who serve on the DSMBAM that might be linked with the study in some way recuse themselves from review of the present study.

The purpose of the DSMBAM is to provide oversight and monitoring of Phase I and Phase II clinical trials of pharmacological and behavioral treatments for stimulant dependence. There are three fundamental charges of the board, which are:

- To ensure the safety of trial participants
- To preserve validity and integrity of research data
- To facilitate the availability of timely as well as reliable findings to the broader clinical community

Below are members who serve as committee chairs as well as clinical research experts:

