15.5 Interim Analysis

There will be no interim analysis

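### Does the outcome report to the monitoring board in Section 14 contradict the statement that there is no interim analysis?

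*Combined protocol and SAP*

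**What the plan says.** Two statements exclude interim analysis. Section 15.5 says "There will be no interim analysis". The synopsis entry on planned interim analyses says "No planned interim analyses. Serious adverse events will be monitored by the committee on an ongoing basis throughout the study".

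Section 14 describes the board's material in three places. The trial's own interim report ends with "a report of AEs and SAES, and the status of outcome data". The account of how the board works says "The DSMC are given blinded trial data, but may request unblinding if safety data warrant". The paragraph that opens "Subsequent ongoing reviews include" closes with the outcome report: "The outcome data report includes outcome data analyzed by group, masked or unblended, with or without statistical analyses, and include all outcome variables".

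Section 8.2 adds that "the identity of test and control treatments will not be known to investigators, research staff, or patients", and keeps the study blind until database lock, patient emergencies apart. It does not mention the board. Section 14 makes the PI and the site physician responsible for "complying with the reporting requirements, including reports to the IRB, DSMB, NIDA" and other bodies.

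Part of Section 14 is absent from the public text, and the separate monitoring plan to which that section refers is not among the documents. Either could give the number of reviews, the report's form or its preparer.

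**The concern.** Taken alone, the outcome-report sentence attaches no condition to any option. Someone preparing a report could follow it literally, test the number of binge drinking days by arm during the trial, and send the result unmasked to the board. A trial that declares no interim analysis would then have had one.

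Three things would be at stake. If the board could act on such a result, the 5% error rate in Section 15.3 would no longer hold, because no alpha is set aside for earlier looks. If unmasked results reached the PI or site physician, their blind would be lost, which matters for an outcome that participants report to staff at weekly visits. And the trial report could not simply state that no interim analysis took place.

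**Working it through.** **1. The four report forms.** Two options for masking and two for statistics give 2 × 2 = 4 forms. Each is set against two rules: no interim analysis (synopsis and 15.5), and blinded data for the board unless safety data prompt a request (Section 14).

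| Form | No interim analysis | Blinded unless safety prompts a request |
|---|---|---|
| Masked, no statistics | fits | fits |
| Masked, with statistics | conflicts if the statistics compare arms | fits |
| Unmasked, no statistics | fits | fits after a safety-driven request |
| Unmasked, with statistics | conflicts if the statistics compare arms | fits after a safety-driven request |

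One form fits without conditions. One is conditional, and its condition stands earlier in the same account of the board. Two conflict only if statistical analyses means between-arm comparison; the phrase also covers summary statistics for each arm. All four are wider than a report on the status of the outcome data, but a wider descriptive report is not a hypothesis test.

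**2. Which statements are specific to this trial.** The outcome-report sentence belongs to a present-tense description of an existing university board, whose purpose Section 14 gives as overseeing trials for stimulant dependence. This is an alcohol trial, so that text reads as the board's standing scope. The statements written for this trial are the synopsis entry, 15.5 and the content of the interim report, and these agree with one another.

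**3. Error rate as written.** Section 15.3 gives a two-sided 5% test with 80% power. With one final test, the error is 2 × (1 − Φ(1.96)) = 0.050, or 2.5% in the direction of false benefit. This reproduces the plan's figure. It holds whatever the board sees, provided nothing seen stops or changes the trial. Stopping for futility could only lower it.

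**4. Error rate if results were acted on (hypothetical).** Let X₁, …, X_K be independent standard normal increments and Z_k = (X₁ + … + X_k)/√k. The error is the probability under the null that |Z_k| > 1.96 at any of K equally spaced looks, the final one included. The documents do not give the number of looks, so K = 2 to 5 is assumed. The first two columns come from numerical integration; simulation with 2,000,000 sequences per K agrees.

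| Looks | Two-sided error | False benefit | Independent looks, 1 − 0.95^K |
|---|---|---|---|
| 2 | 8.3% | 4.2% | 9.75% |
| 3 | 10.7% | 5.4% | 14.3% |
| 4 | 12.6% | 6.3% | 18.5% |
| 5 | 14.2% | 7.1% | 22.6% |

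The last column is an upper bound, since successive looks share data. These figures need both an unadjusted test at each look and a rule to stop on it. The text available contains neither.

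**5. The investigators' blind.** Responsibility for meeting reporting requirements is not the same as preparing or reading the report. Under 8.1 and 8.2 the biostatistician generates the allocation list and identifies the kits at the end, so an unmasked report could go from there to the board without passing through blinded staff.

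**The case for a change.** The best case for a change is that protocol text binds whatever its origin, and nothing in the documents switches off the wider options for this trial. Section 14 also speaks of monitoring efficacy, lists compliance with stopping rules among the items reviewed, and sends the board's recommendations to the investigators, yet no stopping rule or boundary is set out in the text available. The count of one unconditional fit is also lenient: if any by-arm outcome summary counted as an interim analysis, none of the four forms would fit. A few words would settle all this and cost no power.

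The inconsistency of wording stands. What does not follow is a consequence for the result. A recommendation route is not an efficacy rule, and a reference to unstated stopping rules does not authorise stopping on an unadjusted p-value. The cheap remedies also have drawbacks. Holding the board to masked outcome data is debatable, since a board weighing harm may need to see benefit by arm. Declaring interim looks at p<0.001 with a full 5% final test would take the total above the stated 5%: 5.02% to 5.11% for two to five equally spaced looks, and up to 5.29% in the early-clustered schedules tried.

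**Conclusion.** No change to the plan is needed. Section 14 lists more report forms than the rest of the protocol allows, but one form satisfies every statement, a second does so after a safety-driven request, and the statements specific to this trial agree that no interim analysis is planned. The type I error as written is 5.0% two-sided; the 8.3% to 14.2% figures describe a procedure that the plan does not contain. A competent report preparer would send masked descriptive data, unmask on a safety request, and run no efficacy tests. The detailed SAP promised at the start of Section 15 is a natural place to record that.

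This rests on reading the misprinted word as unblinded, on nothing in the absent part of Section 14 or the monitoring plan allowing a stop for efficacy, and on the board not acting on outcome results for efficacy. If the board did so act, the error rate would have to be reconsidered.

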15 STATISTICAL METHODS AND CONSIDERATIONS

Prior to the analysis of the final study data, a detailed Statistical Analysis Plan (SAP) will be written describing all analyses that will be performed. The SAP will contain any modifications to the analysis plan described below.

15.1 Data Sets Analyzed

All eligible patients who are randomized into the study and receive at least one dose of the study drug (the Safety Population) will be included in the safety analysis.

15.2 Demographic and Baseline Characteristics

The following demographic variables at screening will be summarized by treatment group: race, gender, age, educational attainment, employed, and HIV positivity.

15.3 Analysis of Primary Endpoint

To determine the efficacy of targeted naltrexone versus placebo in reducing binge drinking among non-dependent MSM, as determined by number of binge drinking days in timeline follow-back (TLFB), by arm. GEE Poisson models with robust standard errors will be used to assess reductions on weekly drinking outcomes. Baseline TLFB results will be included in the analysis. **Minimum detectable effects (MDEs):**

In calculating minimum detectable effects, we hypothesized on pharmacologic grounds that oral naltrexone will reach full efficacy against alcohol use almost immediately; accordingly we expect treatment-control differences to be approximately constant over the 12 weeks of the trial. Based on the prior trial (93% retention), we estimate that 90% of participants will be retained at 12 weeks. Using estimates based on data from Project ECHO⁹² for the within-subject correlation and over-dispersion of the outcomes, as well as the mean frequency among controls, we estimate that the proposed study will have 80% power in 2-sided tests with a type-I error rate of 5% to detect 27% reductions in numbers of binge drinking occasions, as well as 10% reductions in the average numbers of drinks on drinking days.

To determine the efficacy of targeted naltrexone versus placebo in reducing alcohol consumption among non-dependent MSM, as determined by the proportion of ethyl glucuronide (EtG) positive urines, by arm. GEE logistic models with robust standard errors will be used to assess reductions frequency of positive urine tests, accounting for within-subject correlation. **MDEs:** Using the assumptions for loss to follow-up for Aim 1, as well as estimates based on biomarker data from Batki et al's study on Topiramate for alcohol use disorders¹²² for the within-subject correlation and control group urine positivity rate, we estimate that the study will have 80% power in 2-sided tests with a type-I error rate of 5% to detect 15-23% reductions in the urine positivity rate in the treatment arm.

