9.3.5 Urinalysis

9.3.5.1 Urinalysis for other classes of substance use: Urine samples will be collected weekly and tested for methamphetamine, cocaine, opioids, and other substances of abuse using MEDTOX EZ-SCREEN cups. Positive results will be confirmed by further urine testing through the laboratory at San Francisco General Hospital.

9.3.5.2 Urinalysis for novel alcohol biochemical markers: Urine samples will be collected at enrollment and monthly and tested for ethyl glucuronide (EtG) to determine recent alcohol consumption. EtG is a relatively novel, highly sensitive indicator for recent alcohol consumption; this alcohol biomarker is detectable in urine for approximately 72 hours).¹¹⁸⁻¹²¹ The PI has used EtG to evaluate the efficacy of another pharmacologic intervention in reducing alcohol consumption in a trial funded by the Department of Defense¹²² with [name], a consultant in the proposed study. Urine samples will be tested via liquid chromatography-mass spectrometry through the Redwood Toxicology Laboratory, Inc., the same lab used by [name] ongoing pharmacologic trials on alcohol dependence at the San Francisco Veteran's Affairs Medical Center. EtG quantitative results will be dichotomized using established cutoff values recommended by the Substance Abuse and Mental Health Services Administration (SAMHSA) to distinguish between positive and negative specimens.^{119, 121} Whenever possible we will schedule participants for their weekly visits on Mondays and Tuesdays, given that binge drinking is likely to be higher over the weekend compared to the remainder of the week.

9.3.6 Dried Blood Spot (DSB) Testing for Phosphatidylethanol:

Phosphatidylethanol (PEth)—a phospholipid formed only in the presence of alcohol—is a novel, *direct* biochemical marker of alcohol that has shown high (>95%) sensitivity and specificity to detect heavy drinking over a period of 2-3 weeks in several studies of dependent patients and abstainers. In persons with HIV, recent validation studies found that PEth, using a cutoff of >8 ng/mL, was 88% sensitive and 89% specific for alcohol consumption in the prior 21 days (3 weeks), and 95% sensitive and 73% specific for heavy alcohol consumption (i.e., exceeding the NIAAA cutoffs). DSB samples will be collected at enrollment, weeks 3, 6, 9, 12, and post-

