15.4 Analysis of Secondary Endpoints

The analysis of the secondary endpoint to determine the efficacy of targeted naltrexone versus placebo in reducing alcohol-associated sexual risk behaviors, we will use GEE Poisson models with robust standard errors for the four monthly ACASI assessments on numbers of male anal sex partners, HIV-serodiscordant unprotected anal sex partners, unprotected anal sex partners while intoxicated with alcohol, and unprotected anal sex events with serodiscordant partners, including the baseline value. In the event that these outcomes are severely over-dispersed, we will analyze indicators for any self-report of each behavior, using GEE logistic models. **MDEs:** Based on estimates of within-subject correlation and control prevalence from our Project Echo trial, we estimate that the study will have 80% power to detect 31% reductions in numbers of male anal sex partners, 57% reductions in SDUA partners, 46% reductions in UA partners while intoxicated with alcohol, and 56% reductions in UA events with serodiscordant partners. In analyses using GEE logistic models, we will have 80% power to detect reductions of 14%, 38%, 39%, and 30% in any report of these four sexual risk behaviors, respectively.

Safety and tolerability data will be summarized by treatment group.

Adverse event rates will be coded by body system and MedDra classification term. Adverse events will be tabulated by treatment group and will include the number of patients for whom the event occurred, the rate of occurrence, and the severity and relationship to study drug.

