APPENDIX 1. STUDY PROCEDURES

TABLE 2. Study Procedures

	Visit Type				
	SCR	BL	Wk	Mos. 1 & 2	Mos. 3
Informed consent	X				
Safety lab assessment	X			X	X
Rapid HIV test* or CD4	X				X
HIV risk reduction counseling	X				X
Complete medical history, physical exam & SCID	X				
Vital signs, weight	X	X		X	X
Symptom driven physical exam		X			X
Targeted Medication Training	X				
Text messaging (SMS)			X		
Training			X		
Randomization			X		
Urine testing for opiates	X	X			
Urine testing for ethyl glucuronide (ETG)	X	X	X	X	X
Audio Computer Assisted Survey Instrument (ACASI)		X	X	X	X
Adverse event assessment			X	X	X
Alcohol Use Medical Management Counseling		X	X		

a ±2

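### The Aim 2 EtG model names no baseline term although an enrollment EtG is collected and quantified; pre-specifying it as a covariate is a free gain in precision

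*Combined protocol and SAP*

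**What the plan says.** The synopsis (Statistics, Specific Aim 2) and section 15.3 describe the EtG analysis in the same words: "GEE logistic models with robust standard errors will be used to assess reductions frequency of positive urine tests, accounting for within-subject correlation". Neither mentions a baseline value.

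The other two efficacy models do. For Aim 1, section 15.3 says "Baseline TLFB results will be included in the analysis". For Aim 3, section 15.4 lists the sexual-risk counts and ends "unprotected anal sex events with serodiscordant partners, including the baseline value". Neither says whether baseline is a covariate or one of the repeated outcomes.

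A pre-treatment EtG is available. Section 9.3.5.2 says "Urine samples will be collected at enrollment and monthly and tested for ethyl glucuronide (EtG) to determine recent alcohol consumption", by liquid chromatography-mass spectrometry, and then "EtG quantitative results will be dichotomized using established cutoff values". Section 10.3 collects urine for alcohol testing at the enrollment visit, and Table 2 in Appendix 1 marks EtG at screening and baseline.

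Three other places come close without supplying the term. Section 5.1 says that endpoints are followed over time from baseline, but names no model term. The synopsis plans a sensitivity analysis that adjusts for baseline predictors of missing data. The opening of section 15 promises a detailed SAP before the final analysis.

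**The concern.** EtG is the objective counterpart to a self-reported primary outcome. If a participant's enrollment urine predicts his later ones, leaving it out keeps removable between-person variation in the arm comparison. It also means that any chance difference between two arms of 60 in enrollment positivity is carried partly into the result.

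The silence also leaves a choice open. Adjusted and unadjusted EtG analyses would both be defensible, and they can give different estimates and p-values. Which one counts should be written down before the blind is broken. The same holds for the enrollment urine itself: the text does not say whether it is a covariate, an outcome row or unused.

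**Working it through.** **Inputs from the documents.** 120 participants randomised 1:1, so 60 per arm; 90% retention at 12 weeks, so 54 per arm; two-sided 5% test; 80% power; detectable relative reduction in EtG positivity 15-23% (section 15.3).

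**Inputs assumed.** The plan names a source for the within-subject correlation r and the control positivity rate p but gives no values. I take r from 0.2 to 0.6 and p from 0.7 to 0.9. The number of on-treatment urines m is 3 if collection is monthly (section 9.3.5.2), or 12 if it is weekly (section 10.4, Table 2).

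**The plan's own figure.** Effective n per arm = 54m/(1+(m-1)r), used in the two-proportion formula with pooled null variance. Example: m = 3, r = 0.3 gives 162/1.6 = 101.25. With p = 0.8 and a 22.2% reduction, the rates are 0.800 and 0.622, a difference of 0.178. The requirement is 1.96 x 0.0637 + 0.84 x 0.0625 = 0.177, so power is 80%. Other combinations also fall in or near the stated range:
- m = 3: 15.2% (p 0.9, r 0.2); 23.6% (p 0.8, r 0.4).
- m = 12: 15.2% (p 0.8, r 0.2); 22.3% (p 0.7, r 0.3); 22.4% (p 0.8, r 0.5).

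The 15-23% is therefore attainable but cannot be reproduced uniquely. It is not shown to be wrong.

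**Gain from adjustment (linear approximation, exchangeable correlation).** In units of the single-urine variance, the variance of a participant's mean is (1+(m-1)r)/m. Adjusting for one baseline urine with the same correlation subtracts r². The fraction removed is R² = r²m/(1+(m-1)r). Power that was 80% becomes Φ((1.96+0.84)/√(1-R²) - 1.96).

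| r | m = 3: variance | removed | power | m = 12: variance | removed | power |
|---|---|---|---|---|---|---|
| 0.2 | 0.467 to 0.427 | 9% | 83.4% | 0.267 to 0.227 | 15% | 86.0% |
| 0.3 | 0.533 to 0.443 | 17% | 86.7% | 0.358 to 0.268 | 25% | 89.9% |
| 0.4 | 0.600 to 0.440 | 27% | 90.5% | 0.450 to 0.290 | 36% | 93.7% |
| 0.5 | 0.667 to 0.417 | 38% | 94.3% | 0.542 to 0.292 | 46% | 96.8% |
| 0.6 | 0.733 to 0.373 | 49% | 97.5% | 0.633 to 0.273 | 57% | 98.9% |

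**Check by simulation.** Logistic GEE, exchangeable, robust standard errors, 54 per arm, m = 3, binary baseline covariate, 500 runs per setting.

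| p | reduction | r | unadjusted power | adjusted power |
|---|---|---|---|---|
| 0.8 | 23% | 0.3 | 80% | 88% |
| 0.8 | 23% | 0.5 | 77% | 91% |
| 0.9 | 15% | 0.3 | 74% | 81% |
| 0.7 | 23% | 0.2 | 69% | 71% |

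With no effect (p 0.8, r 0.5), rejection was 4.6% unadjusted and 7.2% adjusted, with Monte Carlo standard error √(0.05 x 0.95/500) = 1.0 point. Part of the simulated gain at r = 0.5 may therefore be small-sample excess in the robust test.

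**Chance imbalance.** At p = 0.8 the SD of the enrollment difference between arms is √(2 x 0.8 x 0.2/60) = 7.3 points, a 95% range of ±14.3. Only about r times a gap carries into follow-up: ±2.9, ±5.7 and ±8.6 points at r = 0.2, 0.4 and 0.6. At the same p, the targeted reductions are 0.15 x 80 = 12 and 0.23 x 80 = 18.4 points.

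This is the same quantity as the precision loss. At r = 0.4 and m = 3, the variance of the unadjusted contrast is (2 x 0.16/60) x 0.600 = 0.00320. The carried imbalance contributes 0.4² x (2 x 0.16/60) = 0.00085, which is 27% of it and matches the table.

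**The case against.** The strongest reply is that nothing is wrong with the analysis as written. Randomisation makes the unadjusted test valid, and the last calculation shows that chance imbalance is already inside its standard error. EtG is a secondary objective (section 3.2), the text excludes nothing, and the promised SAP could add the term. All of this stands, and it limits the point to efficiency and pre-specification.

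Three stronger readings are tempting, and the documents do not support them:
- A reader might infer that the plan rejects baseline for EtG, or that the estimate would be biased. The text is only silent, and the cost is precision.
- A reader might set the ±14-point enrollment range against the 12-point smallest target and conclude that imbalance could swamp the effect. That treats a baseline gap as carrying over in full, when only about r times it does.
- A reader might infer that Aims 1 and 3 already use baseline as a covariate, so that Aim 2 need only match them. Their role for baseline is undefined. Aim 3 counts four monthly surveys, "including the baseline value", while on-treatment monthly visits fall at months 1, 2 and 3, so baseline appears to be one of the repeated outcomes there.

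The size is also open to challenge, and this part stands. Every r and p is assumed. EtG reflects about 72 hours (section 9.3.5.2) and entry requires at least weekly bingeing (section 6.2), so a binary enrollment result may be near ceiling. The calculations treat baseline as correlating with later urines as those do with each other, which is not shown for a log quantitative value.

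**Conclusion.** The point holds as a free improvement. The Aim 2 model names no baseline term, the other two efficacy models say that baseline is included, and the enrollment measurement is already made and quantified.

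Under assumed correlations of 0.2 to 0.5 and three monthly urines, 80% unadjusted power would become roughly 83% to 94%; with twelve weekly urines, 86% to 97%. At 0.2 with monthly urines the gain is only about 3 points, and it could be smaller still with a near-ceiling binary baseline. These figures illustrate scale and do not predict the trial's gain. The textual finding is firm; the size depends on two quantities that the plan does not state.

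**What to change.** In the synopsis (Specific Aim 2) and section 15.3, add one sentence stating that:
- only on-treatment urines are outcomes;
- enrollment EtG enters as a covariate, pre-specified as the log quantitative value, with a rule for results below the assay limit;
- the arm effect is reported as a standardised marginal contrast (risk difference or ratio), because the adjusted odds ratio in a logistic model is conditional and differs from the unadjusted one.

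Name a small-sample correction for the robust standard errors, given the 7.2% null rejection in the simulation. While editing, state the role of baseline for Aims 1 and 3 as well.

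Reconcile section 9.3.5.2 (EtG at enrollment and monthly) with section 10.4 and Table 2 (weekly), since this sets the number of urines per participant and hence the power.

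The cost is a few sentences before unblinding. No new samples or assays are needed for the covariate.
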